5.3 Sample size

We analyzed preliminary data on percent change in hand volume in normal controls as a response to the application of a tourniquet. Similar data is not available in the literature for patients following ALND. In the pilot, the median change was 9.1%, with a standard deviation of 1.6% assuming each subject contributed one baseline hand volume and one volume following the application of the tourniquet.

Our scientific hypothesis is that the difference in change of mean hand volume among women who have had lymph node dissection, between the arms ipsilateral and contralateral to the side of ALND is zero or negligible. We therefore seek a sample size that expresses non-inferiority between ipsilateral and contralateral arms. In the absence of clinical norms for the margin of non-inferiority, we made the sample size calculation on the basis of margin of non-inferiority of 1% (in units of percent change in hand volume).

We plan to accrue 45 extremities in each group, with two arms per patient. We have 90% power that the upper 95% confidence interval of the difference will be at or below the stipulated margin of 1%. A confidence bound above the stipulated margin will be taken as evidence of some difference between ipsilateral and contralateral arms, indicating an effect of the prior axillary lymph node dissection over and above the effect of the tourniquet.

The above calculation assumed a standard deviation of 1.6 percentage point, and 45 patients with two arms each (ipsilateral and contralateral to ALND) to provide 90% power for a margin of equivalence of one percentage point using a two-sided significance level of 5%, with a primary endpoint of percentage change from baseline following tourniquet use. If 10% of patients are uninformative (N=40 for ipsilateral and contralateral arms), we expect have 87% power for the same margin of equivalence. If 20% are uninformative (N=35 for ipsilateral and contralateral arms), we would have 82% power. The secondary outcome of residual limb volume following elevation in the two limb positions (elevated and sling) are not included in this power analysis and are not primary outcomes.

We expect the study to begin upon approval, and conclude after recruitment in approximately 6-12 months.

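### Section 5.3 reads an upper confidence bound above the 1-point margin as evidence of an ALND effect and leaves no room for an inconclusive result

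*Combined protocol and SAP*

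**What the plan says.** Section 5.3 states the aim as non-inferiority: "We therefore seek a sample size that expresses non-inferiority between ipsilateral and contralateral arms". The margin is 1 percentage point of change in hand volume. The success criterion is on the upper limit: "We have 90% power that the upper 95% confidence interval of the difference will be at or below the stipulated margin of 1" per cent.

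The next sentence covers failure to meet it: "A confidence bound above the stipulated margin will be taken as evidence of some difference between ipsilateral and contralateral arms". The same sentence goes on to name ALND as the cause of that difference: "indicating an effect of the prior axillary lymph node dissection over and above the effect of the tourniquet". So there are two outcomes: bound at or below 1, no relevant excess; bound above 1, an effect of ALND. A lower limit is not mentioned.

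Sections 5.0 and 5.2 plan paired t-tests of the ipsilateral against the contralateral arm, and Section 5.0 adds a linear mixed effects model. Neither section attaches a decision rule, and none of the three says whether the bound or the t-test governs the conclusion.

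**The concern.** Failing to exclude a margin is not evidence of a difference. A claim that the ipsilateral arm swells more needs the lower confidence limit above 0. Under the rule as written, imprecision alone (few evaluable patients, a larger SD) can produce a declared ALND effect.

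The bound and the t-test can also part company in two ways:

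- (a) Bound above 1 with p > 0.05: Section 5.3 declares an effect that the t-test does not show.
- (b) Bound at or below 1 with p < 0.05: a difference smaller than the margin, for which the plan has no wording.

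What is at stake is a wrong or self-contradictory statement about the primary outcome. Section 2.0 says patients with prior ALND are commonly steered away from elective hand surgery, so a spurious ALND effect would bear on the question the study is meant to inform. The rule cannot create a false non-inferiority claim, and complications are recorded separately (Section 5.1).

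**Working it through.** **Inputs (Section 5.3).** Margin 1 point; SD 1.6 points; N = 45, or 40 and 35 after losses; true difference 0; stated power 90%, 87%, 82%. The between-arm correlation r is not given, so it is varied. The SD is taken as per arm, because that reading reproduces the stated power.

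**Formulas.** SD of the paired difference = 1.6 × √(2(1 − r)). SE = that SD / √N. Power = P(upper bound ≤ 1 | true difference 0), from the noncentral t with N − 1 df and noncentrality 1/SE. At N = 45, r = 0: SE = 1.6 × √(2/45) = 0.337 and noncentrality = 1/0.337 = 2.96.

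**Step 1: reproduce the stated power (r = 0).**

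| Bound | N=45 | N=40 | N=35 |
|---|---|---|---|
| Stated | 90% | 87% | 82% |
| One-sided 95% | 89.9% | 86.5% | 82.1% |
| Upper limit of two-sided 95% CI | 82.6% | 77.8% | 71.9% |

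The stated figures match a one-sided 95% bound, although the text says "using a two-sided significance level of 5" per cent. The one-sided bound is used below unless noted. If 1.6 were the SD of the paired difference, power at N = 45 would be 99.4% (one-sided) or 98.4% (two-sided CI), which does not match.

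**Step 2: false ALND-effect rate.** At true difference 0 this is P(bound > 1) = 1 − power.

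| r | N=45 | N=40 | N=35 |
|---|---|---|---|
| 0 | 10.1% | 13.5% | 18.0% |
| 0.25 | 4.2% | 6.4% | 9.5% |
| 0.5 | 0.7% | 1.3% | 2.4% |

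The paired t-test makes a false claim in this direction 2.5% of the time. The written rule exceeds that only when r is below about 0.34, 0.42 and 0.50 at N = 45, 40 and 35. If the two-sided 95% CI were meant, the N = 45 rates would be 17%, 8% and 1.6% at r = 0, 0.25 and 0.5.

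**Step 3: one example (N = 45, r = 0).** Observed difference 0.50. One-sided upper bound: 0.50 + 1.680 × 0.337 = 1.07. Two-sided 95% CI: 0.50 ± 2.015 × 0.337 = −0.18 to 1.18; p = 0.15. Section 5.3 declares an ALND effect although the interval includes zero. Both upper limits exceed 1, so the example holds under either reading of the confidence level.

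**Step 4: how often the two analyses disagree (N = 45; 2,000,000 simulated trials per setting).**

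| Event | r=0 | r=0.25 | r=0.5 |
|---|---|---|---|
| (a), true difference 0 | 7.7% | 2.2% | 0.06% |
| (a), true difference 0.5 | 27% | 12% | 0.7% |
| (b), true difference 0.5 | 0.2% | 2.4% | 21% |

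At true difference 0 and r = 0, 7.7 of the 10.1 points, about three quarters, are declared effects with p > 0.05. The rows at 0.5 count disagreements, not false claims, since a difference then exists.

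**The case against.** Four points deserve an answer.

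**Which bound.** The sentence says only a confidence bound. If a lower bound above 1 were meant, the inference would be valid and the rates in Step 2 would not apply. But the sentence directly follows one about the upper limit, so upper is the natural reading. On the other reading, an interval straddling 1 would have no stated interpretation, so the gap remains.

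**Correlation.** Two arms of one patient may well be correlated, and at r = 0.5 the false-claim rate at N = 45 is below 1%. This stands, and it limits the size of the problem. But no correlation is given, and the SD comes from normal controls: "Similar data is not available in the literature for patients following ALND". With an assumed per-arm SD of 2.0, the N = 45 rates would be about 24%, 15% and 5% at r = 0, 0.25 and 0.5. Higher correlation also makes disagreement (b) more common.

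**Link between bound and t-test.** Section 5.0 points to Section 5.3 straight after the mixed-model sentence, so the plan does not expressly tie the bound to the paired analysis. That is fair. A bound from the same paired comparison is the sensible reading, but the plan should say so.

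**Lost sensitivity.** A stricter requirement flags fewer real differences. This also stands, and the cost is given with the fix. The current rule's extra sensitivity comes from treating imprecision as evidence.

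**Conclusion.** The concern holds, and the sentence should be corrected. The logical error does not depend on any assumption; its size does. With SD 1.6 per arm, r = 0 and a one-sided 95% bound, the only combination examined here for the paired analysis that reproduces the stated power, the false ALND-effect rate is about 10% at full enrolment and 18% at N = 35 ("If 20% are uninformative (N=35 for ipsilateral and contralateral arms), we would have 82% power"). It is material mainly at low between-arm correlation, where losses make it worse, and nearly disappears at r = 0.5 with N = 45. Across the correlations examined, the plan lacks wording for at least one kind of disagreement between the bound and the t-test. The harm is confined to the conclusion on the primary volume outcome.

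**What to change.** Replace the sentence with a rule on the paired mean difference (ipsilateral minus contralateral) in percentage change:

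1. One-sided 95% upper bound at or below 1 point: non-inferiority shown.
2. Lower limit of the two-sided 95% CI above 0, which agrees with the paired t-test: evidence that the ipsilateral arm swells more. If (1) also holds, report a difference smaller than the margin.
3. Neither (1) nor (2): inconclusive, with no claim of an ALND effect.
4. Upper limit of the two-sided 95% CI below 0: also report that the ipsilateral arm swelled less.

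State that this paired analysis governs, write down both confidence levels, and correct the two-sided wording for the margin test. Section 5.3 also says "to provide 90% power for a margin of equivalence of one percentage point", so the sponsor should state whether non-inferiority or equivalence applies. Equivalence would also need a lower bound at or above −1; its power at r = 0 is about 80/73/64% at N = 45/40/35 (two one-sided 5% tests).

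**Cost.** A few sentences and an IRB-approved modification. With the one-sided bound in (1), N and the stated power are unchanged. If the two-sided CI is preferred for (1), power at r = 0 becomes about 83/78/72%, and about 56 patients are needed to restore 90%.

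Some results will be labelled inconclusive:

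| Setting | r=0 | r=0.25 | r=0.5 |
|---|---|---|---|
| True difference 0, N=45 | 8% | 2% | 0.06% |
| True difference 0, N=35 | 15% | 7% | 0.9% |
| True difference 0.5, N=45 | 27% | 12% | 0.7% |

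At a true difference of 1 with r = 0, the share of trials flagging a difference falls from 95% to 83% at N = 45 (12% inconclusive) and from 95% to 72% at N = 35 (23% inconclusive). At 0.5 with N = 45 it falls from 57% to 31%. None of the inconclusive results becomes a non-inferiority claim. At r above about 0.34 (N = 45), rule (2) makes more false claims (2.5%) than the current sentence, but the plan already runs that t-test.

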5.0 STATISTICAL CONSIDERATIONS

We will evaluate the data per recommendations of our statistician by categorical and continuous statistical testing, as applicable. For the primary outcomes of percentage change in hand volume from baseline after tourniquet application, and secondary outcome of residual volume as a percentage of baseline following limb positioning, we will compare the healthy contralateral arm versus the arm status post ALND. Paired t-tests will be used to compare measures averaged to produce a single pre-tourniquet hand volume and a single post-tourniquet hand volume. The differences will again be compared between patients' arms ipsilateral and contralateral to the side of ALND. Linear mixed effects model will also be fitted to account for the correlations between measurements on the same subject and history of ALND, arm position after tourniquet use, and patient-specific risk factors. This specific issue power analysis is further discussed below (5.3).

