5.2 Analysis plan

Data will be analyzed as above. To reiterate the methods (Section 4.0), a baseline volume will be measured in all participants prior to tourniquet use. The absolute change in hand volume, percentage change from baseline, and residual volume as a percentage of baseline immediately following tourniquet use will then be measured in all patients. The mean will be compared between the arms ipsilateral and contralateral to the side of ALND by paired t-tests. The parameters listed above are the primary outcomes. Each participant will then be monitored in two limb positions (elevated and sling as described above), with measurements taken on both arms ipsilateral and contralateral to the side of

ALND. Volume is measured after each position. The change in limb edema as a factor of time will be analyzed by a linear mixed effects model. This is the secondary outcome.

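### Section 5.3 states 90/87/82% power at two-sided 5%, but its stated inputs give those figures at one-sided 5%; the confidence limit to set against the 1-point margin is therefore not fixed

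*Combined protocol and SAP*

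**What the plan says.** Section 5.3 sets a non-inferiority margin of 1 percentage point on the percent change in hand volume and takes the true difference between arms to be zero or negligible. The variability comes from a pilot in normal controls, "with a standard deviation of 1.6% assuming each subject contributed one baseline hand volume and one volume following the application of the tourniquet". The decision rule is given with its power: "We have 90% power that the upper 95% confidence interval of the difference will be at or below the stipulated margin of 1" per cent. If the rule fails, "A confidence bound above the stipulated margin will be taken as evidence of some difference between ipsilateral and contralateral arms", and the plan attributes that difference to the prior node dissection.

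The same calculation is then described again as 45 patients with two arms each "to provide 90% power for a margin of equivalence of one percentage point using a two-sided significance level of 5" per cent. Power is put at 87% for N=40, and for the larger loss the plan says: "If 20% are uninformative (N=35 for ipsilateral and contralateral arms), we would have 82% power".

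On the test, Section 5.2 says "The mean will be compared between the arms ipsilateral and contralateral to the side of ALND by paired t-tests", and Section 5.0 also names paired t-tests. Neither section gives a confidence level. No between-arm correlation and no SD of the within-patient difference is stated anywhere.

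**The concern.** Power, level, margin, SD and sample size are tied together: once four are fixed, so is the fifth. Here the stated power looks too high for the stated level, by roughly the amount expected if the calculation was run one-sided at 5% and then described as two-sided.

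The consequence reaches the primary conclusion. The words upper 95% confidence interval can mean a one-sided 95% bound, which fits the power figures. They can also mean the upper limit of a two-sided 95% interval, which fits the stated level. The second limit is always the higher one, so some data sets meet the margin on the first reading and miss it on the second. A miss is not treated as inconclusive; it is read as an effect of the dissection. If the limit is not fixed in advance, that choice can be made after the data are seen.

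**Working it through.** **Inputs.** From Section 5.3: margin 1 point, true difference 0, SD 1.6 points, n = 45, 40 and 35 patients. From Section 5.2: paired t-test. The pilot description makes 1.6 the SD of percent change for a single measurement series per subject, that is, a per-arm SD. Between-arm correlation r: not stated, so r = 0 is taken first and then varied.

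**Formulas.** SD of the difference = 1.6 × √(2(1 − r)). SE = SD of the difference / √n. Power = P(T > t(1−α, n−1)), where T is noncentral t with n − 1 df and noncentrality 1/SE. α = 0.05 is a one-sided 5% test; α = 0.025 corresponds to two-sided 5%.

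**Example, n = 45, r = 0.** SD of the difference = 1.6 × √2 = 2.263; SE = 2.263/√45 = 0.3373; noncentrality = 1/0.3373 = 2.965.

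**Reproducing the plan's figures (r = 0).**

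| | N=45 | N=40 | N=35 |
|---|---|---|---|
| Stated in Section 5.3 | 90% | 87% | 82% |
| One-sided 5%, paired t | 89.9% | 86.5% | 82.1% |
| One-sided 5%, two-sample t (2n − 2 df) | 90.3% | 87.0% | 82.7% |
| Two-sided 5%, paired t | 82.6% | 77.8% | 71.9% |
| Two-sided 5%, two-sample t | 83.5% | 78.8% | 73.2% |

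All three stated figures agree within 1 point at one-sided 5%. At two-sided 5% the paired test falls short by 90 − 82.6 = 7.4, 87 − 77.8 = 9.2 and 82 − 71.9 = 10.1 points.

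**Other readings tried.**
- 1.6 as the SD of the paired difference, two-sided 5%, paired t: 98.4/97.1/94.9%. Too high.
- Equivalence by two one-sided tests, normal approximation, r = 0: 81.3/75.0/66.8% at 5% per side and 68.5/59.6/48.7% at 2.5% per side. Too low.
- Two-sided 5%, paired t, r = 0.21: 90.4/86.6/81.5%. This rounds to the stated figures, but r is fitted to them.

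**Effect on the decision (n = 45, r = 0).** The one-sided 95% bound lies 1.6802 × 0.3373 = 0.567 above the observed difference, so the rule passes if that difference is at most 1 − 0.567 = 0.433. The two-sided 95% limit lies 2.0154 × 0.3373 = 0.680 above it, so the rule passes up to 0.320. These thresholds use the planning SE; in the trial the SE is estimated.

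Any trial that passes the stricter rule also passes the looser one. The chance that the two disagree is therefore the difference in power. With a true difference of 0 and r = 0 it is 89.86 − 82.62 = 7.2% at N=45, 86.46 − 77.81 = 8.7% at N=40 and 82.05 − 71.91 = 10.1% at N=35. A simulation of 200,000 trials agrees (7.2/8.7/10.2%). At N=45 it falls to 3.4% for r = 0.3 and 1.0% for r = 0.5.

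**Power at N=45 by assumed correlation (paired t).**

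| r | 0 | 0.2 | 0.3 | 0.5 |
|---|---|---|---|---|
| One-sided 5% | 90% | 95% | 97% | 99% |
| Two-sided 5% | 83% | 90% | 93% | 98% |

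**The case against.** The strongest reply is that the level may be right and a correlation simply went unreported. The design is within-patient, the test is paired, and Section 5.0 plans a model for correlated measurements. At two-sided 5%, r = 0.21 returns 90/87/82 to rounding, whereas r = 0 at one-sided 5% gives 90/86/82 with the paired test and 90/87/83 with the two-sample test. This stands in part: the numbers alone cannot separate a mislabelled level from an omitted correlation. But no such correlation is documented, and if one was used, its omission is itself the gap.

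Second, the 95% interval and the two-sided 5% level, read together, favour the upper limit of a two-sided interval. That is a fair reading of the words, but the power figures with the stated inputs point the other way, and Sections 5.0 and 5.2 give no level to break the tie.

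Third, Section 5.0 mentions averaging: "Paired t-tests will be used to compare measures averaged to produce a single pre-tourniquet hand volume and a single post-tourniquet hand volume". If each arm has two tourniquet runs, the SD of their mean could be below 1.6; a per-arm SD of 1.43 gives 90% at two-sided 5% with r = 0. Averaging might therefore improve the real power, but it cannot explain the stated figures, because Section 5.3 says that they assumed 1.6.

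Fourth, the practical effect shrinks as correlation rises. That stands, and the true correlation is unknown.

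**Conclusion.** The concern holds. With the inputs that Section 5.3 gives, the stated power does not hold at the stated level: 83/78/72% against 90/87/82%. The figures fit one-sided 5% with zero correlation, or two-sided 5% with an undocumented correlation near 0.2. On either account the section is incomplete, and the limit that decides the primary comparison is open to two readings.

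The result rests on 1.6 being a per-arm SD, as the pilot description implies, on a true difference of 0, and on r = 0 where no other value is named. It does not show that the trial is too small; at r = 0.2 or above, power at N=45 is about 90% or more under either limit. The point should be fixed before the primary comparison is made. Two smaller points are editorial: the margin is called one of equivalence although the rule tests only an upper bound, and a 20% loss from 45 leaves 0.8 × 45 = 36, not 35.

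**What to change.** Keep N=45. Define the difference as ipsilateral minus contralateral, and use one limit in both the power statement and the decision rule.

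- **Option (a), closest to the stated power.** The upper limit of the two-sided 90% confidence interval (one-sided 5%) must be at or below 1 point. Paired t-test, per-arm SD 1.6, between-arm correlation 0: power 90%, 86% and 83% at N=45, 40 and 36 (82% if N=35 is kept). Add power at N=45 of 95%, 97% and 99% for assumed correlations of 0.2, 0.3 and 0.5.
- **Option (b), closest to the stated level.** The upper limit of the two-sided 95% confidence interval (one-sided 2.5%) must be at or below 1 point. Same assumptions: power 83%, 78% and 73% at N=45, 40 and 36 (72% if N=35 is kept). Add 90%, 93% and 98% for the same correlations.

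Under either option, state that 1.6 is a per-arm SD from healthy volunteers. If the calculation used a correlation, give its value and source. Call the margin one of non-inferiority throughout.

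The cost is wording in Section 5.3 only, with no added patients or procedures. Under option (b) the stated power at zero correlation falls by 7 to 10 points if the 45/40/35 sample sizes are kept.

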The purpose of the proposed study is to evaluate the acute impact of swelling caused by low-pressure tourniquet use in the setting of ipsilateral ALND and the change in swelling reduction following tourniquet use in two limb postures, comparing the arms ipsilateral and contralateral to the side of ALND. We hypothesized that tourniquets may be safely applied to patients with prior ALND in either their ipsilateral or contralateral arm. We further hypothesized that patients who have had prior ipsilateral ALND would have an equivalent proportion of upper extremity edema and see improved resolution with increased elevation. Understanding the effect of tourniquet use and its safe practice will aid in the surgical management of patients with prior axillary lymph node dissection.

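### Section 5.3 attaches its power to an equivalence margin, but its only decision rule is a one-directional non-inferiority check, so the stated 90/87/82% are not equivalence powers and passing the rule cannot show equivalence

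*Combined protocol and SAP*

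**What the plan says.** **Hypothesis.** Section 5.3 expects that the difference in mean volume change "between the arms ipsilateral and contralateral to the side of ALND is zero or negligible". Section 2.0 likewise hypothesises that "patients who have had prior ipsilateral ALND would have an equivalent proportion of upper extremity edema". Both statements run in two directions.

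**Design and rule.** Section 5.3 then names a one-directional design: "We therefore seek a sample size that expresses non-inferiority between ipsilateral and contralateral arms", with a "margin of non-inferiority of 1% (in units of percent change in hand volume"). The success rule and its power come together: "We have 90% power that the upper 95% confidence interval of the difference will be at or below the stipulated margin of 1" percent. The failure rule is also one-directional: "A confidence bound above the stipulated margin will be taken as evidence of some difference between ipsilateral and contralateral arms".

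**Power restated.** The next paragraph of 5.3 describes the same calculation with SD 1.6 and 45 patients, but says it serves "to provide 90% power for a margin of equivalence of one percentage point using a two-sided significance level of 5" percent. It gives 87% at N=40 for the same equivalence margin and 82% at N=35.

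**Analysis.** Sections 5.0 and 5.2 plan paired t-tests between the arms. Neither section, nor 5.3, compares a lower confidence limit with -1.

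**The concern.** A non-inferiority rule and an equivalence claim are different tests. The first asks whether the arm on the side of the dissection (the ALND arm) swells no more than 1 point more than the other arm. The second also asks that it swell no more than 1 point less. Equivalence is the harder test and has lower power on the same data. Section 5.3 gives the power of the first test the name of the second.

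Two things are at stake. A reader would take 90% as the chance of demonstrating equivalence, which the plan's inputs do not give. And a trial that passes the upper-bound rule could be reported as confirming an equivalent or negligible difference, although an ALND arm that swells clearly less would pass too. The missing lower bound matters at any significance level; the two-sided 5% label is a further inconsistency in the same sentence.

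**Working it through.** **Inputs.** From 5.3: SD 1.6 percentage points, margin 1, N = 45, 40 or 35 patients with two arms each. From 5.0 and 5.2: paired t-test, so N-1 degrees of freedom. Assumptions: true difference 0, in line with the hypothesis; 1.6 is a per-arm SD, since the pilot figure is a change from baseline and not a between-arm difference; within-patient correlation ρ = 0 to start, because the documents give none.

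**Standard error.** SD of the difference = 1.6 × √(2(1-ρ)), which is 2.263 at ρ = 0. SE = SD of the difference / √N = 0.337, 0.358 and 0.382. The noncentrality 1/SE is 2.965, 2.795 and 2.615.

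**Step 1: reproduce the plan's figures.** Power for the upper bound alone = P(noncentral t with N-1 df and noncentrality 1/SE exceeds the one-sided critical t).

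| Upper bound only, ρ = 0 | N=45 | N=40 | N=35 |
|---|---|---|---|
| Stated in 5.3 | 90% | 87% | 82% |
| One-sided 5%, paired df | 89.9% | 86.5% | 82.0% |
| One-sided 5%, two-sample df | 90.3% | 87.0% | 82.7% |
| One-sided 2.5% (two-sided 5%), paired df | 82.6% | 77.8% | 71.9% |

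With uncorrelated arms the stated figures match the single-bound test at one-sided 5%, and not at two-sided 5%.

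**Step 2: equivalence on the same inputs.** Both confidence limits must lie within -1 to +1 (two one-sided tests). With a true difference of 0 the two ways of failing are equally likely and practically never occur together, so power ≈ 2 × (single-bound power) - 1. For N=45 at 5% per side: 2 × 0.899 - 1 = 0.798. Exact integration over the sample variance gives:

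| Both bounds, ρ = 0, paired df | N=45 | N=40 | N=35 |
|---|---|---|---|
| 5% per side (90% interval) | 79.7% | 72.9% | 64.1% |
| 2.5% per side (95% interval) | 65.2% | 55.6% | 43.9% |

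**Step 3: dependence on the correlation.** The same calculation with assumed ρ, at 5% per side:

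| Both bounds | N=45 | N=40 | N=35 |
|---|---|---|---|
| ρ = 0.25 | 92% | 87% | 81% |
| ρ = 0.5 | 99% | 97% | 95% |

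At 2.5% per side and N=45 the values are 83% (ρ = 0.25) and 97% (ρ = 0.5).

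**Step 4: could an unstated correlation rescue the labels?** At ρ = 0.21 the upper bound alone at one-sided 2.5% gives 90.4/86.6/81.5%, close to the stated figures. So the two-sided 5% label could be right if such a correlation had been used, but 5.3 does not mention one. Even then this is single-bound power. Equivalence power at ρ = 0.21 and 5% per side is 89.9/85.1/78.4%, which matches at N=45 but not at 40 or 35.

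**Step 5: what the rule lets through.** Suppose the ALND arm truly swells 2 points less (N=45, ρ = 0). The true difference then lies 3/0.337 = 8.9 standard errors below +1, and the upper-bound rule passes in more than 99.9% of trials. A two-bound rule passes in fewer than 0.01%.

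**The case against.** The strongest reply is that 5.3 names its design. It says non-inferiority, states an explicit upper-bound rule, and attaches 90% to that rule. The later equivalence sentence describes the same calculation, so it can be read as a loose label. A one-directional rule also suits a safety question: less swelling in the ALND arm is no sign of harm. This stands. For the upper-bound rule at one-sided 5%, 90% is correct, and the rule should stay primary. But the reply does not cover the hypotheses in 5.3 and 2.0, which non-inferiority alone cannot confirm.

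Second, a reader might infer that the trial has only 80% power where it needs 90%. The documents do not support that. The 80% requires zero correlation, a true difference of exactly 0 and 5% per side. The arms belong to the same patient and the analysis is paired; at a correlation of about 0.22, equivalence power at N=45 already reaches 90% (5% per side).

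Third, a reader might infer that a clear negative difference would go unseen. It would not. In the example of 2 points less, the noncentrality is 2/0.337 = 5.9, and the planned paired t-test, taken at two-sided 5%, would reject zero difference in more than 99.9% of trials. Nor do the documents state that passing the rule will be reported as equivalence. What remains is that the decision rule would pass such a result and no rule ties the equivalence wording to a test that could refute it.

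**Conclusion.** The point holds as an inconsistency between hypothesis, decision rule and stated power. The 90% and 87% are assigned to equivalence at two-sided 5%, but on the stated inputs they are non-inferiority powers at one-sided 5%. With SD 1.6 per arm, true difference 0 and uncorrelated arms, the overstatement for an equivalence claim at N=45 is about 10 percentage points at 5% per side (90% against 80%), and about 25 if two-sided 5% means a 95% interval (90% against 65%). It widens to 18 and 38 points at N=35 (82% against 64% and 44%).

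These figures correct the plan's calculation and say nothing firm about the actual paired power, which depends on a correlation the documents do not give. The missing lower bound does not depend on that correlation: under the rule as written, success supports no more than the statement that the ALND arm swells at most 1 point more.

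**What to change.** Keep the upper-bound rule as the primary decision and amend 5.3 before analysis:

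1. Replace *equivalence* with *non-inferiority* as the name of the margin in both places, and tie 90/87/82% to the upper-bound rule.
2. Replace the two-sided 5% level with the one-sided 5% level at which those powers hold. Alternatively keep two-sided 5% and restate the powers as about 83/78/72%, or document the correlation that justifies higher values.
3. Word the conclusion on success as: the ALND arm swells no more than 1 percentage point more than the contralateral arm.
4. Add that an equivalent, or zero or negligible, difference will be claimed only if both confidence limits lie within -1 to +1, and state the interval's level. Give its power as conditional on the within-patient correlation: 80/73/64% at correlation 0 and 5% per side, with a range for higher assumed values (for example 92% at 0.25 and 99% at 0.5 for N=45).
5. Align the hypothesis in 2.0 with this wording.

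The cost is protocol text and one further comparison with an interval already computed. The stated power for any equivalence claim becomes less favourable and openly dependent on an assumption. No additional patients or measurements are needed.
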